## List of Abbreviations

**AE:** Adverse event  
**AE SI:** Adverse event of special interest  
**AFT:** accelerated failure time  
**ANC:** Absolute neutrophil count  
**BMI:** body mass index  
**CCH:** Chester County Hospital  
**CDI:** *Clostridium difficile* infection  
**CFR:** Code of federal regulations  
**CFU:** colony-forming units  
**CRC:** clinical research coordinator  
**DSMB:** Data safety monitoring board  
**EIA:** enzyme immunoassay  
**FMT:** Fecal Microbiota Transplantation  
**g:** grams  
**HIPAA:** Health Insurance Portability and Accountability Act of 1996  
**HUP:** Hospital of the University of Pennsylvania  
**ICH:** International Conference on Harmonisation  
**IDSA:** Infectious Diseases Society of America  
**ITT:** intention to treat  
**LGH:** Lancaster General Hospital  
**mL:** milliliters  
**m-ITT:** modified intention to treat  
**PAH:** Pennsylvania Hospital  
**PHI:** protected health information (PHI)  
**PMPMC:** PennMedicine Princeton Medical Center (PMPMC)  
**PMT:** Penn Microbiome Therapy  
**PPI:** proton pump inhibitor  
**PPMC:** Penn-Presbyterian Medical Center  
**R-CDI:** Recurrent *Clostridium difficile* infection  
**SAE:** Serious Adverse Event  
**S/SC/F-CDI:** severe or severe-complicated/fulminant *Clostridium difficile* infection  
**SIRS:** systemic inflammatory response syndrome  
**SUSAR:** Suspected unexpected serious adverse reaction  
**WBC:** white blood cells

## Study Summary

Title	A Phase II, Randomized Trial to Evaluate the Safety and Efficacy of Fecal Microbiota Transplantation using the Penn Microbiome Therapy Products for Severe or Severe-Complicated/Fulminant Clostridium difficile Infection
Short Title	PMT for Severe-CDI
IRB Number	832962
Phase	Phase II
Methodology	Randomized, open label, comparative
Study Duration	Two years
Study Center	PennMedicine - University of Pennsylvania Health System
Objectives	
Primary: To evaluate the efficacy of fecal microbiota transplantation (FMT) performed using the Penn Microbiome Therapy (PMT) suite of products to treat subjects with severe and severe-complicated/fulminant Clostridium difficile infection (S/SC/F-CDI) by comparing the clinical outcomes of three treatment strategies: (1) no investigational product (standard of care only); (2) upper gastrointestinal administration FMT in addition to standard of care; (3) lower gastrointestinal FMT in addition to standard of care.
 
Secondary: To evaluate the safety of the PMT suite of investigational products for use in treating S/SC/F-CDI.
 
Exploratory: To characterize (1) the baseline gut bacterial community composition and host immune phenotype associated with S/SC/F-CDI, (2) the change in gut bacterial community composition and host immune phenotype associated with each of the above treatment strategies, and (3) to determine the relationship between baseline gut bacterial community composition, host immune phenotype, and treatment outcome in patients with S/SC/F-CDI.

Number of Subjects	Target enrollment: 90 subjects

**Inclusion Criteria:**

1. One or more episodes of CDI with symptoms including bowel movements altered in frequency or consistency from baseline.
2. Stool test positive for *Clostridium difficile* by EIA by FDA-cleared assay within 7 days prior to enrollment.
3. Age  $\geq$  18 years.
4. Meeting criteria for S/SC/F-CDI within 72 hours of enrollment, which we define as any one of the following: (1) leukocytosis with peripheral WBC  $\geq$  15,000 cells/mL; (2) hypotension with systolic blood pressure sustained  $<$  90mmHg for three or more hours or requiring pressors; (3) provider documentation of ileus or radiologic evidence of bowel dilation or megacolon; (4) acute kidney injury with increase in baseline serum creatinine level by  $\geq$ 50% or new dialysis initiation; (5) serum lactate  $>$  2.2 mmol/L; or (6)  $\geq$  3 systemic inflammatory response syndrome (SIRS) criteria (which include heart rate  $>$  90 beats per minute, respiratory rate  $>$  20 breaths per minute or PaCO2  $<$  32 mmHg, temperature  $>$ 38°C or  $<$ 36°C, WBC  $>$  12,000 cells/uL,  $<$ 4,000 cells/uL, or  $>$ 10% immature (band) forms).
5. Receiving antibiotic treatment for S/SC/F-CDI per current IDSA guidelines (i.e., vancomycin or fidaxomicin).

**Main Inclusion  
and Exclusion  
Criteria****Exclusion Criteria:**

1. Evidence of colon/small bowel perforation at the time of study screening.
2. Goals of care are directed to comfort rather than curative measures.
3. Moderate (ANC  $<$  1000 cells/uL) or severe (ANC  $<$  500 cells/uL) neutropenia.
4. Known food allergy that could lead to anaphylaxis.
5. Pregnancy
6. Receipt of FMT or enrollment in a clinical trial for FMT within the last 3 months.
7. COVID-19 infection, as defined by a positive nucleic acid or antigen test within the prior 14 days and symptoms consistent with COVID-19 infection

**Investigational Product**

1. Penn Microbiome Therapy – 001 (PMT-001): no more than 152mL suspension for rectal enema from 40g human stool, comprising a total of  $1 \times 10^8$  –  $1 \times 10^{12}$  anaerobic bacterial CFUs/dose.
2. Penn Microbiome Therapy – 002 (PMT-002): no more than 152mL suspension for intragastric, intraduodenal, or intrajejunal administration from 40g human stool, comprising  $1 \times 10^8$  –  $1 \times 10^{12}$  anaerobic bacterial CFUs/dose.
3. Penn Microbiome Therapy – 003 (PMT-003): no more than 32 capsules for oral administration from 40g donated stool, comprising  $1 \times 10^8$  –  $1 \times 10^{12}$  anaerobic bacterial CFUs/dose.

PMT-001, PMT-002, PMT-003 are packaged for single-dose administration.

**Duration of administration**

10 – 90 minutes (target 30 minutes)

**Reference therapy**

Standard of care antibiotics as prescribed by treating clinician. (Must be concordant with current IDSA guidelines to be eligible for enrollment).

**Statistical Methodology**

Primary outcome will be time to resolution of severe symptoms. We will compare both FMT groups (i.e., upper and lower gastrointestinal administration) in aggregate versus the standard of care group via competing risk regression model.

**Safety Evaluations**

We will monitor safety of administration as well as safety of the investigational products, in terms of adverse events as listed in [Section 9](#).

**Data and Safety Monitoring Plan**

See [Section 10](#).

## Background and Study Rationale

This study will be conducted in full accordance all applicable University of Pennsylvania Research Policies and Procedures and all applicable Federal and state laws and regulations including 45 CFR 46, 21 CFR Parts 50, 54, 56, 312 and Good Clinical Practice: Consolidated Guidelines approved by the International Conference on Harmonisation (ICH). All episodes of noncompliance will be documented.

### 1. Introduction

Fecal microbiota transplantation (FMT) is recommended treatment for recurrent *Clostridium difficile* infection (R-CDI) based on its success in multiple trials targeting subjects with mild or moderate CDI symptoms (McDonald 2018; Kelly BJ 2018). Though there have been only small, observational studies and case series of FMT for patients with severe and severe complicated/fulminant CDI, these suggest that FMT may also be of benefit in severe and severe complicated/fulminant CDI (S/SC/F-CDI) as well (Weingarden 2013; Agarwal 2015; Aroniadis 2015; Fischer 2015; Fischer 2017). We will perform a randomized controlled trial to evaluate the safety and efficacy of Penn Microbiome Therapy (PMT) products for FMT in subjects who meet criteria for S/SC/F-CDI. The PMT products comprise three different formulations of FMT for oral, enteric (via tube), or rectal delivery. The S/SC/F-CDI trial will compare the efficacy of PMT with standard of care antibiotic therapy to standard of care antibiotic therapy alone. We will also assess the safety of PMT in this study population. Finally, we will characterize key microbiome and host immune phenotype features associated with S/SC/F-CDI disease and recovery in an exploratory fashion. The planned study will inform treatment recommendations for S/SC/F-CDI and lay the groundwork for novel CDI risk stratification and S/SC/F-CDI prevention strategies.

#### 1.1. Background and Relevant Literature

As recently as 2015, the Centers for Disease Control and Prevention (CDC) identified *Clostridium difficile* infection (CDI) as an “urgent” threat associated with upwards of 500,000 infections in the United States each year and resulting in over 15,000 deaths. CDI is characterized by a clinical syndrome that typically includes loose, frequent bowel movements and abdominal pain, which occur as a result of toxin production by colonic *C. difficile*. CDI occurs in patients colonized with toxigenic *C. difficile* and in patients who have newly acquired *C. difficile*. Estimates of the relative contributions of persistent colonization and new acquisition to incident CDI vary. In both cases, the pathogenesis of CDI involves depletion of non-*C. difficile* colonic microbiota, altered bile acid metabolism, germination of (resident or recently ingested) *C. difficile* spores, expansion of a population of vegetative *C. difficile*, toxin production, and colonic inflammation. Key challenges associated with CDI include its recurrence after appropriate antibiotic treatment (R-CDI), and its progression to a more severe disease state with systemic signs of inflammation or even sepsis. The latter, termed severe or severe-complicated/fulminant CDI (S/SC/F-CDI), often requires extended hospitalizations, may require colectomy, and is associated with high rates of mortality (Kelly BJ 2018). At present, antibiotic treatment is the recommended therapy for early R-CDI, and antibiotic treatment followed by FMT is the recommended therapy for later R-CDI. Antibiotics alone are the recommended therapy for S/SC/F-CDI (McDonald 2018), but observational studies suggest a benefit for FMT in the S/SC/F-CDI population as well (Weingarden 2013; Agarwal 2015; Aroniadis 2015; Fischer 2015; Fischer 2017).

## 1.2. *Name and Description of the Investigational Product*

### Penn Microbiome Therapy suite of investigational products

- Penn Microbiome Therapy – 001, hereafter referred to as PMT- 001,
  - Dose:  $1 \times 10^8$  –  $1 \times 10^{12}$  anaerobic bacterial CFUs derived from 40g of human stool diluted with 10% glycerol into no more than 152 mL suspension of investigational product.
  - Enema administered rectally.
- Penn Microbiome Therapy – 002, hereafter referred to as PMT - 002,
  - Dose:  $1 \times 10^8$  –  $1 \times 10^{12}$  anaerobic bacterial CFUs derived from 40g of human stool diluted with 10% glycerol into no more than 152 mL suspension of investigational product.
  - Suspension administered intragastric, intraduodenal, or intrajejunal.
- Penn Microbiome Therapy – 003, hereafter referred to as PMT - 003,
  - Dose:  $1 \times 10^8$  –  $1 \times 10^{12}$  anaerobic bacterial CFUs derived from 40g of human stool diluted with 10% glycerol and concentrated to fill no more than 32 capsules.
  - Capsules to be administered orally.

### Chemical Name and Structure:

PMT-001: Fecal Microbiota for Transplant, enema product

PMT-002: Fecal Microbiota for Transplant, suspension product

PMT-003: Fecal Microbiota for Transplant, capsule product

The three investigational products, PMT-001,002, 003, are composed of donated stool from healthy donors that meet the donation criteria. The stool sample is composed of approximately 75% water and 25% organic and inorganic solids. Typically, 1g of stool contains approximately  $10^9$  bacterial cells. The stool sample is subsequently processed with phosphate-buffered saline (PBS) containing 10% glycerol and formulated as a suspension for PMT-001 and PMT-002 or concentrated and encapsulated for PMT-003.

#### **1.2.1. Non-Clinical Data**

FMT as a treatment modality for CDI did not take the conventional path of drug development. Fecal transplants seem to date as far back as 4th century China, and have recently become recommended therapy for R-CDI on the basis of several randomized trials (McDonald 2018; van Nood 2013; Youngster 2016; Kelly CR 2016; Kao 2017), even as there remains significant heterogeneity among FMT products. There is no established standard for non-clinical testing of FMT products given uncertainty as to what microbial features determine potency (Bojanova 2016). The treatment protocol outlined here is based on the results published from prior studies that have driven the standards adopted in our R-CDI and S/SC/F-CDI protocols (Hamilton 2012; Kelly BJ 2018; Cammarota 2017; Krajicek 2018).

### **1.2.2. Clinical Data to Date**

There is no available clinical research data to date on the investigational products PMT-001, 002, or 003. FMT has been established as effective and is recommended for treatment of multiply recurrent CDI on the basis of several randomized controlled trials (McDonald 2018; van Nood 2013; Youngster JAMA 2014; Kelly CR 2016; Kao 2017). Observational studies have suggested that FMT may have similar efficacy for S/SC/F-CDI (Weingarden 2013; Agarwal 2015; Aroniadis 2015; Fischer 2015; Fischer 2017). See [Table 1](#) for a summary of the risks described in the literature.

**Table 1: FMT dosing and associated risks**

Authors	Publication Year	Population	Study Design	FMT Dose (g stool)	FMT Formulation	FMT Administration	Risks
Hamilton et al	2012	R-CDI	single-group trial	50g stool	250mL suspension	colonoscopy	diarrhea, flatulence
van Nood et al	2013	R-CDI	randomized trial	(not reported)	500mL suspension	duodenal tube	diarrhea, cramping, belching
Youngster et al JAMA	2014	R-CDI	single-group trial	48g stool	30 capsules	oral	cramping, bloating
Kelly et al	2016	R-CDI	randomized trial	64g stool	500mL suspension	colonoscopy	chills, abdominal pain, bloating, nausea, flatulence
Kao et al	2017	R-CDI	randomized trial	80-100g stool	40 capsules or 180mL suspension	oral or colonoscopy	nausea, vomiting, fever, abdominal discomfort
Weingarden et al	2013	S/SC/F-CDI	case series	50g stool	250mL suspension	colonoscopy	(not reported)
Agrawal et al	2015	S/SC/F-CDI	case series	~30-60g stool	150-500mL suspension	upper endoscopy, lower endoscopy, enema	diarrhea, constipation, abdominal pain, ileus
Aroniadis et al	2015	S/SC/F-CDI	case series	(not reported)	suspension	upper endoscopy, lower endoscopy, enema, colonoscopy	diarrhea, abdominal pain
Fischer et al	2015	S/SC/F-CDI	case series	50-100g stool	300mL suspension	sigmoidoscopy or colonoscopy	treatment failure and death
Fischer et al	2017	S/SC/F-CDI	case series	50-100g stool	300mL suspension	sigmoidoscopy or colonoscopy	treatment failure and death

### **1.3. Dose Rationale**

There are no pre-clinical or clinical data for the PMT suite of FMT products to inform optimal dose. However, there are extensive observational studies and several randomized trials that suggest an FMT dose derived from 30-100g of human stool is effective to treat R-CDI (Cammarota 2014; van Nood 2013; Youngster JAMA 2014; Kelly CR 2016). Protocols for the treatment of S/SC/F-CDI have typically used similar FMT doses as protocols for the treatment of R-CDI, but have allowed for repeat FMT administration at short intervals if clinically indicated (Weingarden 2013; Agarwal 2015; Aroniadis 2015; Fischer 2015; Fischer 2017). See [Table 1](#) for a summary of doses described in the literature.

The S/SC/F-CDI trial protocol allows for repeat PMT dosing at 3-day intervals, up to a maximum of three doses, if subjects fail to meet pre-established criteria for clinical improvement. The repeat administration strategy is based on the observation that some patients with S/SC/F-CDI fail to improve with initial FMT administration but do improve after repeat administration (Weingarden 2013; Agarwal 2015; Aroniadis 2015; Fischer 2015; Fischer 2017).

## **2. Study Objectives**

### **2.1. Primary Objective**

To evaluate the efficacy of fecal microbiota transplantation (FMT) performed using the Penn Microbiome Therapy (PMT) suite of products to treat subjects with severe and severe-complicated/fulminant *Clostridium difficile* infection (S/SC/F-CDI) by comparing the clinical outcomes of three treatment strategies: (1) no investigational product (standard of care only); (2) upper gastrointestinal administration FMT in addition to standard of care; (3) lower gastrointestinal FMT in addition to standard of care.

### **2.2. Secondary Objective**

To evaluate the safety of the PMT suite of investigational products for use in treating S/SC/F-CDI.

### **2.3. Exploratory Objective**

To characterize (1) the baseline gut bacterial community composition and host immune phenotype associated with S/SC/F-CDI, (2) the change in gut bacterial community composition and host immune phenotype associated with each of the above treatment strategies, and (3) to determine the relationship between baseline gut bacterial community composition, host immune phenotype, and treatment outcome in patients with S/SC/F-CDI.

## **3. Investigational Plan**

### **3.1. General Design**

We will perform a randomized, controlled, open label trial. Subjects will be screened to evaluate if they meet inclusion criteria for severe or severe complicated/fulminant CDI. If eligible, subjects will participate in the informed consent process. Following informed consent, subjects

will be randomized to one of three arms: (1) standard of care antibiotics (no intervention), (2) PMT-upper GI administration plus standard of care antibiotics, or (3) PMT-lower GI administration plus standard of care antibiotics. Subjects will then be eligible to receive up to two additional administrations of PMT (upper or lower GI) at 3-day (+/- 1 day) intervals if they do not meet pre-defined criteria for clinical improvement (see [Section 3.2.1](#) below). Subjects will be followed until 180 days after their last PMT dose.

### **3.1.1. Screening Phase**

Potential subjects will be identified by active surveillance for inpatients at participating hospitals with positive *C. difficile* EIA stool testing. A positive stool EIA test for *C. difficile* will prompt review of the electronic health record to determine whether a potential subject may meet inclusion/exclusion criteria. If a potential subject may meet inclusion/exclusion criteria, the study team will contact the subject's inpatient care team to ascertain whether the care team has any objection to the study team approaching the potential subject. If the potential subject's care team has no objection, the potential subject (or their designated medical decision-maker) will be contacted to discuss participation, final screening for inclusion/exclusion criteria will be performed, and informed consent will be obtained. A record of all screened subjects will be maintained to evaluate the frequency of identified exclusions or care-team objections. The study will also be open to patients transferred to a participating hospital who had positive (FDA cleared) *C. difficile* EIA stool testing at an outside hospital prior to transfer, so long as a record of the positive test can be obtained. Care teams at the participating hospitals may refer such patients for participation.

### **3.1.2. Study Intervention Phase**

All S/SC/F-CDI trial interventions will be performed inpatient at the listed study site hospitals. During the intervention period, following informed consent and randomization, subjects in either the upper GI (PMT-002 or PMT-003) or lower GI (PMT-001) intervention arm will receive single-dose PMT administration, with PMT formulation and route of administration (suspension for enema, suspension for enteric delivery, or oral capsules) determined per randomization and stratification scheme ([Section 3.1.6](#)). Administration of the product will take place over 10 to 90 minutes (target 30 minutes). Subjects randomized to PMT will be eligible to receive up to two additional administrations of PMT (by clinically appropriate route of administration) at 3-day (+/- 1 day) intervals, if they fail to meet criteria for clinical improvement ([Section 3.2.1](#)). Antibiotics prescribed as part of routine clinical care for CDI will not be altered by the intervention.

### **3.1.3. Post-PMT Administration monitoring: Bedside for 60 Minutes**

Subjects will be monitored at 30 and 60 minutes following completion of PMT administration. Subjects will be visually observed for signs of aspiration or other respiratory distress (PMT-002 and PMT-003), abdominal pain, vomiting, other signs of allergic reaction, and changes in vital signs (PMT-001, PMT-002, and PMT-003). Vital signs (temperature, heart rate, respiratory rate, blood pressure, and oxygen saturation) will be checked. The following vital sign changes will be recorded if observed, and will prompt notification of the primary clinical care team: (1) heart rate increase or decrease by greater than or equal to 30 beats per minute; (2) respiratory rate increase or decrease by greater than or equal to 10 breaths per minute or if respiratory rate drops below 10 or increases above 25 (if respiratory rate not already outside these ranges); (3) temperature:

increase or decrease by greater than or equal to 2 degrees Fahrenheit, or if temperature drops below 96°F or increases above 100.4°F (if temperature not already outside these ranges); (4) oxygen saturation decrease by greater than or equal to 5% (sustained for more than 20 seconds) or if oxygen saturation drops below 90% (on current amount of oxygen delivered, sustained for more than 20 seconds); (5) blood pressure decrease by more than 30 mmHg systolic or 15 mmHg diastolic, or if blood pressure drops below 90/60 (if blood pressure not already outside these ranges).

#### **3.1.4. Post-PMT Administration monitoring: Daily for 3 Days after Administration/Enrollment**

The subject will be monitored every calendar day for three days after each PMT administration in order to assess their eligibility for repeat up to 2 additional doses of PMT at 3 days after the first administration and 3 days after a second administration (if given), as well as to assess for adverse events. If the subject continues to meet criteria for severe or severe-complicated disease within the prior 24 hours at 3 days after the initial administration and then 3 days after the second administration (if given), the subject will be eligible for a repeat dose of PMT (same formulation as per initial randomization). If PMT administration is unable to be performed at 3 or 6 days following the first administration, then administration within 1 calendar day before or after those days will be permitted. Assessment for eligibility for an additional dose will be performed on the day of repeat administration. For subjects in the non-PMT arm, monitoring will be performed daily for three days after enrollment for adverse event assessment.

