**Figure 1: Allocation to Interventional Group Flow Diagram**

### 3.2. Study Endpoints

#### 3.2.1. Primary Study Endpoints

The primary outcome is resolution of symptoms associated with S/SC/F-CDI, listed below. The primary outcome will be satisfied when the subject is discharged from the hospital (not to hospice or palliative care) or, while the subject remains hospitalized, when the following criteria are met for 72 hours:

- If radiology study or studies performed, ileus/dilation/megacolon either not noted or noted as resolved (electronic medical record search words: “ileus”, “dilated”, “dilation”, or “megacolon”)
- Ileus/megacolon either noted as resolved by any provider documentation or not noted (electronic medical record search words: “ileus”, “megacolon”)
- WBC < 15,000 cells/uL
- Serum creatinine decreased, unchanged, or increased by  $\leq 0.2$  mg/dL over 72 hours (if not receiving continuous renal replacement therapy (CRRT) or hemodialysis (HD))
- Lactate  $\leq 2.2$  mmol/L (if measured by clinical care team)
- No vasopressors used (including epinephrine, norepinephrine, phenylephrine, or vasopressin)
- Temperature  $< 38.5$  °C and  $\geq 35.6$  °C
- < 8 bowel movements per day and < 600 mL unformed stool (if volume recorded)
- Meeting fewer than 3 systemic inflammatory response syndrome (SIRS) criteria (i.e., no more than two of the following: heart rate > 90 beats per minute; respiratory rate > 20 breaths per minute or PaCO2 < 32 mmHg; temperature > 38°C or < 36°C; WBC > 12,000 cells/uL, < 4,000 cells/uL, or > 10% immature (band) forms)

Discharge to hospice, need for bowel surgery (colectomy, diverting ileostomy), and death will count as failures. Subjects who undergo bowel surgery after initial PMT administration will not be eligible for additional administrations.

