### 5.2. Intervention Regimen

This study is a randomized, controlled, open label trial. Subjects will be screened to evaluate if they meet inclusion criteria for severe or severe complicated/fulminant CDI. If eligible, subjects will participate in the informed consent process. Following informed consent, subjects will be randomized to one of three arms: (1) standard of care antibiotics (no intervention), (2) PMT-upper GI administration plus standard of care antibiotics, or (3) PMT-lower GI administration plus standard of care antibiotics. In the intervention arms, subjects will then be eligible to receive up to two additional administrations of PMT (upper or lower GI) at 3-day intervals if they do not meet pre-defined criteria for clinical improvement for 24 hours (see [Section 2.1](#)). If PMT administration is unable to be performed on the scheduled days (3-day intervals), administration within 1 calendar day before or after those days will be permitted. Subjects will be assessed for eligibility for an additional dose on the day of repeat administration. Subjects will be followed until 180 days after their last PMT dose.

During the intervention period, following informed consent and randomization ([Section 3.1.2](#)), subjects in either intervention arm (not the standard of care control arm) will receive single-dose PMT administration, with PMT formulation determined per randomization. Administration of the product is described in [Section 5.7](#) below. Subjects will be eligible to receive up to two additional administrations of PMT (per same randomization) at 3 days and 6 days (+/-1 day) after the initial dose if they fail to meet criteria for clinical improvement ([Section 3.2.1](#)) and as long as they do not have bowel surgery. Antibiotics prescribed as part of routine clinical care for CDI will not be altered by the intervention.

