#### **6.2.4. Post-Intervention 3 Days**

The subject will be monitored every calendar day for three days after each PMT administration in order to assess their eligibility for repeat up to 2 additional doses of PMT at 3 days after the first administration and 3 days after a second administration (if given) as well as to assess for adverse events. If the subject continues to meet criteria for severe or severe-complicated disease within the prior 24 hours at 3 after the initial administration and 3 days after a second administration (if given) (see [Section 3.2.1](#)) and if the subject has not undergone bowel surgery, the subject will be eligible for an additional dose of PMT (formulation per repeat assessment of subject's mode of nutrition and medication – i.e., change in formulation is allowed). If PMT administration is unable to be performed on the scheduled days, administration within 1 calendar day before or after those days will be permitted. Subjects will be assessed for eligibility for an additional dose on the day of repeat administration. Subjects in the non-PMT arm will be monitored every calendar day for three days after enrollment to assess for adverse events.

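### The trigger for a repeat PMT dose is stated inconsistently: differing look-back periods, two non-matching criteria lists, and a reference to a section that holds no criteria

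*Combined protocol and SAP*

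**What the plan says.** The rule for a second or third dose appears in several places.

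- **Failing the Section 3.2.1 criteria.** Section 3.1 makes subjects eligible "if they do not meet pre-defined criteria for clinical improvement", and Section 3.1.2 "if they fail to meet criteria for clinical improvement". Both point to Section 3.2.1, as does the second paragraph of Section 5.2. None gives its own look-back. Section 3.2.1 defines the primary endpoint. It is satisfied by discharge (other than to hospice or palliative care) or, "while the subject remains hospitalized, when the following criteria are met for 72 hours".
- **Severity criteria, 24 hours.** Section 3.1.4 makes eligible a subject who "continues to meet criteria for severe or severe-complicated disease within the prior 24 hours". The severity criteria are in Section 4.1 and Table 2. Section 6.2.4 uses the same phrase but refers the reader to Section 3.2.1.
- **Improvement criteria, 24 hours.** The first paragraph of Section 5.2 makes subjects eligible "if they do not meet pre-defined criteria for clinical improvement for 24 hours" and cites Section 2.1. That section is the primary objective and contains no criteria.

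Sections 1.3 and 6.2.2 mention failure to improve with neither a window nor a reference. A repeat dose falls 3 days after the previous one, with one calendar day allowed either side. Bowel surgery ends eligibility.

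**The concern.** The number of doses, one to three, is part of the intervention. If the sections select different subjects, exposure in the FMT arms depends on which section the study team works from. The product has no prior clinical data (Section 1.2.2), and the trial is open label.

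Two further uses of the rule need a single version. Section 8.6 plans a per-protocol analysis and Section 7.9.1 requires deviations to be identified; neither can be applied to re-dosing while the trigger is unsettled. The follow-up visits in Section 3.1.5 and Table 3 are timed from the last dose, so they move with the dose count.

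**Working it through.** **1. Is there a figure to reproduce?** No. The documents state no expected share of subjects re-dosed. The main check is therefore a comparison of the texts.

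**2. Do the lists agree?** Section 3.2.1 and Section 4.1/Table 2 use the same thresholds for white cells, lactate, temperature and SIRS count. They differ on three items.

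- Stool: Section 3.2.1 requires fewer than 8 movements a day and, if volume is recorded, less than 600 mL unformed. The severity list has no stool item.
- Blood pressure: the severity list counts systolic pressure below 90 mmHg sustained for three or more hours, or vasopressor use. Section 3.2.1 looks only at vasopressors.
- Kidney: the severity list counts a creatinine rise of at least 50%, or new dialysis. Section 3.2.1 asks only that creatinine has not risen by more than 0.2 mg/dL over 72 hours.

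**3. Who is eligible at day 3?** The middle column supposes that the criteria missing from Section 2.1 are those of Section 3.2.1.

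| Subject, nothing else abnormal | Fails 3.2.1, 72 h read literally | Fails 3.2.1 list, 24 h (5.2, first paragraph) | Severity criteria, 24 h (3.1.4) |
|---|---|---|---|
| Clear on both lists for at least 24 but under 72 hours | Eligible | Not | Not |
| 8 or more stools a day | Eligible | Eligible | Not |
| Systolic below 90 for 3 hours, no vasopressors | Not, if otherwise clear for 72 h | Not | Eligible |
| Creatinine stable, still at least 50% above baseline, no dialysis | Not, if otherwise clear for 72 h | Not | Eligible |

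Each pair of columns disagrees for at least one kind of subject. The last three rows separate the two 24-hour columns, so fixing the look-back at 24 hours would not by itself remove the conflict.

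**4. How much could the look-back matter?** This needs an assumption. Let T be the time from first dose until the subject is free of all criteria, exponential with mean m. Take m = 2 and m = 4 days, the FMT-arm durations in the two headline cases of Section 8.4 (4 to 2 days, 7 to 4 days).

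The exponential form is compatible with the power table. With 90 events, 2:1 allocation and hazard ratio equal to the duration ratio, the two-sided Schoenfeld formula at type I error 0.2 gives:

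- 4 to 2 days: Φ(√(90 × 1/3 × 2/3) × ln 2 − 1.28) = 0.965, stated 0.97
- 7 to 4 days: Φ(√20 × ln 1.75 − 1.28) = 0.889, stated 0.90

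This shows consistency with the plan's figures. It is not evidence about actual recovery times.

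At a check 3 days after the first dose:

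- 24-hour look-back: eligible if T > 2, share exp(−2/m). For m = 2, exp(−1) = 0.37; for m = 4, exp(−0.5) = 0.61. Of 60 FMT subjects, about 22 or 36.
- 72-hour window read literally: eligible if T > 0, share 1.00.

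Over means of 1 to 5 days the 24-hour share runs from 14% to 67%; taking 1 to 5 days as medians, from 25% to 76%.

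The day of the check matters. At day 2, which the window permits, 72 clear hours cannot have accrued since the dose. At day 4 the shares are exp(−3/m) against exp(−1/m): 22% against 61% for m = 2, and 47% against 78% for m = 4.

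**The case against.** The strongest reply is that no section states a 72-hour look-back for re-dosing. The sections citing 3.2.1 can be read as borrowing its list, with the 72 hours belonging to the primary endpoint alone. Every section that does give a re-dosing look-back says 24 hours, and Section 6.2.4 itself ties the severity wording to Section 3.2.1. Daily monitoring for eligibility would also serve little purpose if nearly everyone qualified. On this reading there is one list and one 24-hour window.

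That is a reasonable reading, and it removes most of the numerical contrast. It does not settle the matter. No section says that the 72 hours are to be ignored when 3.2.1 is cited. Section 3.1.4 carries no reference to 3.2.1 and uses the language of the enrolment categories. The list differences remain at 24 hours, and the Section 2.1 reference still leads nowhere.

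A reader might infer more than the documents support:

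- **That all three statements would re-dose very different shares.** Only the 72-hour against 24-hour contrast can be sized, and only by assumption. Nothing in the documents sizes the difference between the two 24-hour wordings.
- **That nearly every FMT subject would get a second dose under the 72-hour reading.** Discharge satisfies Section 3.2.1 and dosing is inpatient only, so discharged subjects drop out. Surgery ends eligibility. Enrolment looks back 72 hours, so some subjects may have no criterion present at first dose. Mean dose counts per FMT subject built on 100% would ignore all this.
- **That separate sites would diverge.** Section 4.5 describes one site with six locations. Divergence is possible but not shown.
- **That endpoints would shift with the last dose.** Section 3.2.2 times several secondary endpoints from last FMT, but Section 8.2 times those same endpoints from enrolment. The primary outcome has no last-dose anchor.

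**Conclusion.** The inconsistency stands on the text. The trigger points to a list whose in-hospital criteria must hold for 72 hours in some sections, to severity criteria over 24 hours in others, and to a section without criteria in one. The two lists classify some subjects in opposite ways, so eligibility depends on the section followed even if every section is read with a 24-hour look-back.

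The size is conditional. About 100% against roughly 37% (mean 2 days) or 61% (mean 4 days) at day 3 holds only if the 72-hour window is taken literally, durations are exponential, and the subject is still in hospital, not operated on, and had a criterion present at first dose. If all sections are read with 24 hours, the effect reduces to the list differences, which the documents do not allow anyone to size. The point should be corrected because the rule sets exposure to the product and the correction is cheap; it does not show that the primary comparison is invalid.

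**What to change.** Reconcile Sections 3.1, 3.1.2, 3.1.4, 5.2 (both paragraphs), 6.2.2 and 6.2.4 to one trigger, one criteria list and one look-back period, stated once and cited elsewhere. Correct the reference to Section 2.1 in the first paragraph of Section 5.2, and the reference to Section 3.2.1 beside the severity wording in Section 6.2.4. If the chosen rule draws on Section 3.2.1, say whether its 72 hours apply to re-dosing. Which rule, list and window should stand is for the sponsor; this review does not propose one.

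The cost is amendment wording, with no change to sample size or to the primary analysis model. If subjects have already been re-dosed, record which section's rule was applied to each, so that the per-protocol analysis can be defined.
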